### 8.4.5 Adverse Event Reporting

The Principal Investigator or delegated AI is responsible for detecting, documenting, and reporting unanticipated problems, adverse events (AEs), including serious adverse events (SAEs), and deviations in accordance with NIH policy, IRB requirements, and federal regulations. Relatedness to the research of all serious adverse events will initially be determined by the PI or delegated AI in consultation with the IMM. Final determinations will be made by the DSMB in conjunction with the sponsor. All high-grade AEs (grade 3 and above) and all SAEs will be forwarded to the IMM and the DSMB within 2 business days, regardless of initial determination.

The IMM and DSMB should receive the written initial determination and justification from the PI at the time of initial reporting. The IMM and DSMB will receive updates from the PI regarding potential changes to expectedness or relatedness, and safety, within 48 hours, but not later than 7 days.

All AEs (serious and non-serious) that are either related or possibly related to research procedures; protocol deviations; and unanticipated problems will be summarized and reported at the time of continuing review.

# 8.4.6 Serious Adverse Event Reporting

The study investigator will immediately (but no later than 24 hours) report to the sponsor any serious adverse event, whether or not considered study intervention related, including those listed in the protocol or investigator brochure and must include an assessment of whether there is a reasonable possibility that the study intervention caused the event. Study endpoints that are serious adverse events (e.g., all-cause mortality) must be reported in accordance with the protocol unless there is evidence suggesting a causal relationship between the study intervention and the event (e.g., death from anaphylaxis). In that case, the investigator must immediately report the event to the sponsor.

All serious adverse events (SAEs) will be followed until satisfactory resolution or until the site investigator deems the event to be chronic or the participant is stable. Other supporting documentation of the event may be requested by the study sponsor and should be provided as soon as possible.

The study sponsor will be responsible for notifying the Food and Drug Administration (FDA) of any unexpected fatal or life-threatening suspected adverse reaction as soon as possible, but in no case later than 7 calendar days after the sponsor's initial receipt of the information. In addition, the sponsor must notify FDA and all participating investigators in an Investigational New Drug (IND) safety report of potential serious risks, from clinical trials or any other source, as soon as possible, but in no case later than 15 calendar days after the sponsor determines that the information qualifies for reporting.

# 8.4.7 Events of Special Interest

The following are defined as Events of Special Interest (ESI). Once identified, they follow the algorithm outlined in Appendix 2 and separate HAC charter.

- Increase in alanine transaminase (ALT) > 3xULN
- Increase in aspartate transaminase (AST) > 3xULN
- Increase in total bilirubin Level (TBL) > 2xULN

Expedited (<15 days) reports will be sent to the FDA for any cases with transaminases >8x ULN or >3x ULN with total bilirubin >2x ULN.

### 8.4.8 Reporting of Pregnancy

Pregnancy of a female participant as well as pregnancy occurring in a female partner of a male participant is reported as an AE and is qualified and reported as an SAE only if it fulfills one of the seriousness criteria (Section 8.4.2). In the event of pregnancy in a female participant, tolebrutinib should be discontinued. Follow up of the pregnancy in a female participant or in a female partner of a male participant is mandatory until the outcome has been determined.

# 8.5 UNANTICIPATED PROBLEMS

# 8.5.1 Definition of Unanticipated Problems (UP)

Any incident, experience, or outcome that meets **all** of the following criteria:

- Unexpected in terms of nature, severity, or frequency given (a) the research procedures that are described in the protocol-related documents, such as the Institutional Review Board (IRB)-approved research protocol and informed consent document; and (b) the characteristics of the participant population being studied; and
- Related or possibly related to participation in the research ("possibly related" means there is a reasonable possibility that the incident, experience, or outcome may have been caused by the procedures involved in the research); and
- Suggests that the research places participants or others (which many include research staff, family members or other individuals not directly participating in the research) at a greater risk of harm (including physical, psychological, economic, or social harm) than was previously known or expected.

### 8.5.2 Unanticipated Problem Reporting

The investigator will report unanticipated problems (UPs) to the NIH Institutional Review Board (IRB) as per Policy 801.

# 8.5.3 NIH Intramural IRB Reporting of IND Safety Reports

Only IND Safety Reports that meet the definition of an unanticipated problem will need to be reported to the NIH Intramural IRB.

# 9 STATISTICAL CONSIDERATIONS

No separate Statistical Analysis Plan has been developed for this protocol.

# 9.1 STATISTICAL HYPOTHESIS

- Primary Endpoint: The per-participant proportion of lesions in which the paramagnetic rim has disappeared at the end of 48 weeks of tolebrutinib 60 mg treatment is >0.01.
- Secondary Endpoints:
  - Tolebrutinib 60 and 120 mg doses are safe and tolerable in the study population.
  - The T1 relaxation time has decreased in paramagnetic rim lesions at the end of 96 weeks of tolebrutinib 120 mg, relative to non-rim lesions.
  - The size of paramagnetic rim lesions has diminished at the end of 96 weeks of tolebrutinib 120 mg, relative to non-rim lesions.

# 9.2 SAMPLE SIZE DETERMINATION

Given our previous natural history data, which indicates that only 1 out of 29 individuals experienced subtle changes in at least one paramagnetic rim lesion over a period of  $\sim$ 5 years, we expect that very few to no participants in the non-tolebrutinib cohort will experience changes in this study and conservatively

estimate this null proportion to be 0.01. Although even a single tolebrutinib-cohort participant experiencing short-term changes would potentially be clinically meaningful, we have powered this study to detect disappearance of at least one paramagnetic rim lesion in 2 out of 7 completers (expected proportion: 0.29). In this scenario, the interval of (0.0367, 0.7096) will have 95% probability to include the true proportion. Thus, the null hypothesis will be rejected if 2 participants experience at least one lesion change.

To recruit 7 study completers in tolebrutinib Cohort A, we expected to enroll 10 prospective participants into that cohort. As of May 2023, the first 7 participants had completed 48 weeks of tolebrutinib 60 mg, so no additional participants will be recruited into this Cohort. Participants in the non-tolebrutinib comparison cohort (up to 10) will not be replaced if they drop out. We expect the total study duration, including the long-term extension (beyond Week 144 for Cohort A, to be approximately 5 years from the time of first dosing.

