performed on a variety of scanners on less sensitive 3T MRI systems, so results at 7T MRI with the advanced sequences used in this protocol cannot be fully extrapolated. The lack of a strong efficacy signal even in the preliminary analysis of LTS16004, along with good tolerability of the 120-mg dose in TDR16862, justified escalation of the treatment dose for participants in this protocol.

Since no drug has yet been shown to resolve chronic active white matter lesions, and since disappearance of paramagnetic rim lesions has not previously been used as an outcome measure in clinical trials, the timing of the study visits at which efficacy outcomes are measured is somewhat arbitrary. As mentioned above, chronic active lesions are established on the order of 3–6 months following initial demyelination, so that 48 weeks at the target dose is a reasonable time point at which to measure the primary outcome. Additional measurements will be taken at 24, 72, 96, 120, and 144 weeks (the last two in Cohort A) to determine the time course of rim disappearance and any associated promotion of lesion repair. Following the initial 96 weeks of tolebrutinib 60 or 120 mg therapy, participants will be eligible to continue therapy, with monitoring visits every 24 weeks (or more frequently if clinically necessary), either until tolebrutinib is marketed or until its development is halted.

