### 6.1.1.3 *Devices*

The primary 7-tesla MRI scanner and relevant accessories, as well as the pulse sequences used in this study, are FDA-approved, and their use conforms to the corresponding FDA labels.

If for any reason the primary 7-tesla MRI scanner is not available, another 7-tesla or (less preferred) 3tesla scanner may be used under conditions designated by the FDA as constituting nonsignificant risk under 21 CFR 812.2(b)(1). Acquisition parameters may be modified within the permitted range. These studies may also involve image reconstruction and analysis software, including research pulse sequences. In addition, the following non-FDA-approved systems may be used in this study under conditions designated by the FDA as constituting nonsignificant risk, with assurances from the manufacturer that all measures found in FDA-approved MRI are operational.

Justification for MRI, image reconstruction and analysis software, and head coil non-significant risk (NSR) designation

- Magnetic resonance imaging system (7T and 3T MRI) operating in research mode and with research pulse sequences
- MAGNETOM 7T scanner (manufactured by Siemens)
- Image reconstruction and analysis software
- 1Tx 32Rx Head Coil (manufactured by Nova Medical; tested and supplied by Siemens)

According to 21 CFR 812.3 (m) and FDA "Information Sheet Guidance for IRBs, Clinical Investigators, and Sponsors: Significant Risk and Nonsignificant Risk and Nonsignificant Risk Medical Device Studies January 2006," the use of these devices in the study are a Non-significant Risk study. 21 CFR 812.3(m) enumerates four criteria for a Significant Risk Device Study; none of these apply to this study:

- is intended as an implant and presents a potential for serious risk to the health, safety, or welfare of a subject.
  - None of the devices are implants.
- is purported or represented to be for a use in supporting or sustaining human life and presents a potential for serious risk to the health, safety, or welfare of a subject.

37

None of the devices are for use in supporting or sustaining human life.

• is for a use of substantial importance in diagnosing, curing, mitigating, or treating disease, or otherwise preventing impairment of human health and presents a potential for serious risk to the health, safety, or welfare of a subject.

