# 9.4 STATISTICAL ANALYSES

9.4.1 General Approach

# 9.4.2 Analysis of the Primary Endpoint

The primary outcome is the per-patient proportion of lesions in which the paramagnetic rim has disappeared at the end of 48 weeks of tolebrutinib 60 mg/day, in comparison to the scan just prior to initiation of tolebrutinib dosing. Such participants can be in Cohort A or the Initial Cohort (combined analysis). Proportion of diminished/resolved paramagnetic rims is analyzed by investigators blinded to time point, reported descriptively, and compared to the assumption of no change off therapy via a binomial exact test. The analysis will be performed in study completers, and by definition no data will be missing. A threshold p-value of 0.05 will be taken as a significant change.

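### The primary rim test is given different units, events and nulls in Sections 9.1, 9.2 and 9.4.2, so the same data can pass or fail

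*Combined protocol and SAP*

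**What the plan says.** All places are in the combined protocol and SAP. Section 9 states that no separate SAP exists, so its subsections carry the whole analysis.

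- **Section 9.1** takes the per-participant proportion of lesions whose rim has disappeared and hypothesises that this quantity "at the end of 48 weeks of tolebrutinib 60 mg treatment is >0.01".
- **Section 9.2** starts from natural history (1 of 29 people with subtle changes over about 5 years) to "estimate this null proportion to be 0.01". It powers the study on disappearance of at least one rim in 2 of 7 completers, then states that "the null hypothesis will be rejected if 2 participants experience at least one lesion change".
- **Section 9.4.2** first names the per-patient proportion of lesions with a disappeared rim. The test sentence then reads "Proportion of diminished/resolved paramagnetic rims is analyzed by investigators blinded to time point", with the result "compared to the assumption of no change off therapy" by a binomial exact test at 0.05. The value 0.01 is not repeated. The section adds that the analysis is in completers and "by definition no data will be missing".

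Three other places bear on this:

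- **Section 6.1.1.3** says that if the primary 7T scanner is unavailable, "another 7-tesla or (less preferred) 3tesla scanner may be used".
- **Section 4.3** describes rim measurements in another study as "performed on a variety of scanners on less sensitive 3T MRI systems".
- **Section 7.1.2** removes participants who are off tolebrutinib for more than 12 weeks from the primary analysis.

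**The concern.** A confirmatory test needs one unit, one event and one null. Here each of the three changes between subsections. An exact binomial test needs a count of successes out of a number of trials; a fraction of lesions within each person does not supply one. The event moves from disappearance to any lesion change to diminished or resolved. The null is 0.01 in 9.1 and 9.2 but attached to different quantities, and 9.4.2 puts it as no change.

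At stake is whether the trial's single primary verdict is fixed before the rims are read. The study is open-label, and by May 2023 all seven participants had completed 48 weeks. A choice left open at this stage could be made, or appear to be made, with the results in view.

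**Working it through.** **Reproducing the plan's figure.** The exact (Clopper-Pearson) 95% limits for 2/7 solve P(X ≥ 2 | 7, L) = 0.025 and P(X ≤ 2 | 7, U) = 0.025. They give L = 0.0367 and U = 0.7096, as stated in 9.2. Since 0.01 lies below L, 2 of 7 rejects.

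**The wordings side by side.**

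| Place | Unit | Event | Null |
|---|---|---|---|
| 9.1 | lesions within a person | disappeared | 0.01 |
| 9.2 | participant | disappearance (power); lesion change (rule) | 0.01 |
| 9.4.2, endpoint sentence | lesions within a person | disappeared | none given |
| 9.4.2, test sentence | not stated; the test needs a count | diminished or resolved | no change |

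**Exact p-values, participant as unit, n = 7, null 0.01.**

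- P(X ≥ 1) = 1 − 0.99^7 = 1 − 0.9321 = 0.068.
- P(X ≥ 2) = 1 − 0.99^7 − 7(0.01)(0.99^6) = 1 − 0.9321 − 0.0659 = 0.002.

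The critical count is therefore 2. Section 9.4.2 does not state whether the test is one- or two-sided, but at this null the two exact p-values coincide.

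**Case A, the event.** Two participants have fainter but visible rims, and no rim disappears anywhere. Under 9.4.2's test sentence this is 2/7, p = 0.002, reject. Under disappearance it is 0/7, p = 1, do not reject.

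**Case B, the null.** One participant loses a rim. At 0.01 this is 1/7, p = 0.068, do not reject. If no change is taken literally as a null of zero, one event has probability 0 under the null and rejects.

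**Is 0.01 too low?** The rule's type I error is P(X ≥ 2 | 7, p).

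- Setting it to 0.05 gives p = 0.0534.
- 1/29 = 0.0345 unscaled gives 0.022.
- Scaled to 48 weeks at constant hazard (assumed), 1 − (28/29)^((48/52)/5) = 0.0065 gives 0.0009.
- The exact upper 95% limit of 1/29 is 0.178; scaled the same way it is 0.035, which gives 0.023.

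Every figure drawn from natural history on the 48-week scale lies below 5.3%.

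**Evaluable number.** At 0.01, P(X ≥ 1) is 0.068 with 7, 1 − 0.99^6 = 0.059 with 6, and 1 − 0.99^5 = 0.049 with 5. The critical count stays at 2 with six evaluable and would fall to 1 with five.

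**The case against.** The best defence is that the documents already point to one reading. The synopsis (Section 1.1) gives the primary outcome measure as loss of at least one baseline rim. Section 3 places rims that have diminished or disappeared among the exploratory endpoints. Sections 9.1 and 9.2 share 0.01, and 9.2 explains it as a cautious number for expecting very few or no changes, so 9.4.2's null may be the same idea in prose. All of this stands. It shows which reading to adopt, but it does not remove the contrary wording from the sentence that specifies the test.

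A reader might infer more than the documents support:

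- **That the plan leaves field strength open.** It does not. The primary objective names 7-tesla MRI, the schedules place it at baseline and week 48, and no 3T use is reported. The gap is narrower: nothing bars the 3T fallback in 6.1.1.3 from deciding rim status. With a 7T baseline and a 3T follow-up, lower sensitivity would err toward a vanished rim; a 3T baseline would instead miss rims.
- **That type I error is inflated.** The figures above do not show this. The 85–90% rater agreement in Section 2.2.1 is not a rate of false disappearance, and the documents give no such rate.
- **That pooling lesions would turn one person's two lost rims into a rejection.** At 0.01 this holds with 35 or fewer rims in total (p = 0.048 at 35, 0.050 and above the threshold at 36). Those totals, and independence of rims within a person, are assumed; 9.2's explicit rule counts participants.

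**Conclusion.** The inconsistency is real and should be corrected, although its importance is modest. On identical data the event wording moves the result between p = 0.002 and 0/7, and the null wording moves a single responder between p = 0.068 and rejection. Both cases are hypothetical results that show sensitivity to wording; neither demonstrates an error in the trial. Case B also depends on reading 9.4.2 literally.

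The null of 0.01 and the 2-of-7 rule need no change. The rule holds 0.05 up to a participant-level background rate of 5.3%, against a scaled upper limit of 3.5% from natural history. That comparison rests on constant hazard and on the 1-of-29 figure, which concerns subtle changes and not disappearance. Only an unmeasured reading-error rate could push the background above 5.3%.

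The 3T and missing-data points are secondary tidying of the same paragraph.

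**What to change.** Issue a dated clarification before the masked read is opened.

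1. In 9.1, 9.2 and 9.4.2, state that the exact binomial test has the participant as its unit, at least one baseline rim disappeared at week 48 as its event, and 0.01 as its null, and that it rejects at 2 or more of 7.
2. In the test sentences of 9.2 and 9.4.2, replace lesion change and diminished/resolved with disappeared. Report the per-participant lesion proportion as the endpoint estimate, and diminished rims descriptively.
3. Add to 9.4.2 that rim status for the primary endpoint is read on 7T scans only, in line with the objective and schedule, so that the fallback in 6.1.1.3 cannot decide it.
4. Reconcile "by definition no data will be missing" with the exclusion in 7.1.2. Also show the result with any non-evaluable participant counted as no disappearance (denominator 7). With five evaluable, a single event would give 0.049 on five and 0.068 on seven; both should then be reported.

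Showing p-values over several nulls, or reading the scans masked to cohort as well as time point, is optional. Neither is needed to repair a within-person test that is already to be read masked to time point.

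The cost is minor: wording and one sensitivity line, with no change to visits, sample size, null or threshold. The drawback is timing. The clarification would post-date the week-48 visits of all seven participants and should be disclosed as such.

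### Section 9.2 calls the study powered at 0.29 but gives no power (its rule yields about 64–65%); the tolebrutinib headcounts and the null in 9.4.2 also need reconciling

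*Combined protocol and SAP*

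**What the plan says.** Section 9.2 sets the null proportion at 0.01 and continues: "we have powered this study to detect disappearance of at least one paramagnetic rim lesion in 2 out of 7 completers (expected proportion: 0.29". Its justification is "In this scenario, the interval of (0.0367, 0.7096) will have 95% probability to include the true proportion", followed by "Thus, the null hypothesis will be rejected if 2 participants experience at least one lesion change". The document gives no numerical power, and Section 9 says that no separate SAP exists.

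Section 9.1 states the primary hypothesis for the per-participant proportion of lesions whose rim "has disappeared at the end of 48 weeks of tolebrutinib 60 mg treatment is >0.01". Section 9.4.2 says "Proportion of diminished/resolved paramagnetic rims is analyzed by investigators blinded to time point" and that the result is "compared to the assumption of no change off therapy" by an exact binomial test at 0.05. Sidedness is not stated.

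On numbers, Section 9.2 says "To recruit 7 study completers in tolebrutinib Cohort A, we expected to enroll 10 prospective participants into that cohort", and then "As of May 2023, the first 7 participants had completed 48 weeks of tolebrutinib 60 mg", so recruitment has stopped. The Study Description in the synopsis (1.1) says 16 adults will initiate tolebrutinib. The Study Population paragraph and Section 6.3 say up to 10. The synopsis also reports that 7 started, of whom 4 consented to Cohort A and 3 remain at 60 mg. Section 9.4.2 pools the two cohorts for the primary analysis.

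**The concern.** Power is the probability of meeting the rejection rule when a stated alternative is true. Section 9.2 instead takes an observed result of 2/7, shows that its interval excludes 0.01, and calls the study powered. Setting the alternative equal to the smallest rejecting result cannot give high power, because a result below that cut-off remains quite likely.

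This matters for reading a negative result. Someone told that the study is powered at 0.29 may take 0/7 or 1/7 as evidence against an effect of that size. Under the plan's rule, that outcome has a 36% chance when the true proportion is 2/7.

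Two further points affect the same calculation. The headcounts in the current text cannot all be right. The null described in 9.4.2 is not the one that produces the cut-off of 2.

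**Working it through.** **Inputs.** From 9.2: n = 7, null 0.01, alternative 2/7 (rounded there to 0.29), reject at X ≥ 2. From 9.4.2: exact binomial test, threshold 0.05. X is the number of participants with at least one qualifying rim change, as in 9.2.

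**1. The plan's own figures.** The exact (Clopper–Pearson) 95% interval for 2/7 is (0.0367, 0.7096), which matches 9.2. For the cut-off at null 0.01:

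- P(X ≥ 1) = 1 − 0.99^7 = 0.068, so one event does not reject at 0.05.
- P(X ≥ 2) = 1 − 0.99^7 − 7(0.01)(0.99^6) = 1 − 0.9321 − 0.0659 = 0.0020, so two events reject.

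The one- and two-sided exact p-values coincide for both results, so the unstated sidedness does not affect the cut-off. Attained type I error is 0.2%.

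**2. Power of that rule.** Power = 1 − (1−p)^7 − 7p(1−p)^6.

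- p = 2/7: 1 − 0.0949 − 0.2656 = 0.640
- p = 0.29: 1 − 0.0910 − 0.2600 = 0.649
- 80% is reached at p ≈ 0.371, and 90% at p ≈ 0.453

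**3. What a negative result excludes.** The two-sided exact 95% upper limits are 0.41 for 0/7 and 0.58 for 1/7. Neither excludes 0.29.

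**4. Sensitivity to the evaluable number.** Section 7.1.2 removes from the primary analysis anyone off tolebrutinib for more than 12 weeks, so 48-week completion does not by itself guarantee 7 evaluable participants. With 6:

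- Null 0.01: P(X ≥ 1) = 1 − 0.99^6 = 0.059, so the cut-off stays at 2.
- Power at 2/7: 1 − (5/7)^6 − 6(2/7)(5/7)^5 = 1 − 0.1328 − 0.3187 = 0.548.

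**5. Sensitivity to the null.** With n = 7 and one-sided 0.05, the cut-off remains 2 for any null from about 0.0073 to 0.053. That range covers both 0.01 and 1/29 = 0.034, the natural-history figure in 9.2. It does not cover 0. Against a literal null of 0, a single event rejects, and power at 0.29 would be 1 − 0.71^7 = 0.909.

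**6. Headcounts.**

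| Place | Number on tolebrutinib |
|---|---|
| 1.1, Study Description | 16 to initiate |
| 1.1, Study Population; 6.3 | up to 10 |
| 1.1, Study Description; 9.2; 9.4.6 | 7 started; no more can be recruited |
| 1.1; footnotes in 1.2 and 1.3 | Cohort A 4, others 3 (4 + 3 = 7) |
| 1.1, Study Population; 9.2 | target of 7 completers in Cohort A |

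Sixteen equals none of 7, 10, 7 + 10 = 17 or 10 + 10 = 20. Seven completers cannot all belong to a cohort of 4. In addition, Initial Cohort covers all 7 starters in the synopsis, but only those who did not escalate in the schedule of activities.

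**The case against.** The strongest reply is that 9.2 contains no wrong number. The interval and cut-off are exact, the basis is shown openly, and no power level is claimed that could be false. That stands: the fault is an unsupported word and a missing figure.

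It can also be said that little turns on it. All 7 have completed 48 weeks, recruitment is closed, results will also be reported descriptively, and the printed interval already reaches 0.71. This limits the consequence but does not remove it, because the wording will still frame how 0/7 or 1/7 is read. A reader might infer that the trial should have had 10 completers, since the same rule gives 82.7% at 2/7 with 10 and 77.7% with 9. The documents set no 80% target, and the number cannot now be raised, so that inference supports no request.

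A third objection is that the 64% belongs to a participant-level yes/no event, whereas 9.1 and 9.4.2 describe a per-participant proportion of lesions. The event also shifts between disappearance, lesion change, and diminished or resolved rims. This stands, and the power statement must be conditional on the definition chosen.

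Finally, the Cohort A target in 9.2 is in the past tense and may record the plan before escalation was removed. The synopsis can also be read as 7 starters of whom 4 later moved to Cohort A. That explains the labels, but the Study Population paragraph still states the Cohort A target as current.

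**Conclusion.** The claim that the study is powered at 0.29 is not supported by what 9.2 offers. Under its own rule, power is about 64–65% between 2/7 and 0.29, and about 55% at 2/7 if only 6 are evaluable. These figures assume independent participants, a participant-level event, a null of 0.01 and rejection at 2 or more.

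The headcounts of 16, up to 10 and 7 conflict in current text, and the target of 7 does not fit a Cohort A of 4. A reader might infer that the primary analysis set is therefore wrong. It is not: 9.4.2 pools the cohorts, and 4 + 3 gives the 7.

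A reader might also infer from 9.4.2 that a single event suffices. Sections 9.1 and 9.2 fix 0.01 and require two, so this is a mismatch in wording to be closed rather than evidence of a different test. The matter should be corrected, but it does not invalidate the test.

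**What to change.** 1. **Section 9.2.** Replace the powered-to-detect statement with: *If all 7 completers are evaluable and the event is participant-level (at least one rim lesion meeting the chosen event definition), rejecting at 2 or more against a null of 0.01 has attained type I error 0.2% and power of about 64% at 2/7 and 80% at about 0.37 (about 55% at 2/7 if only 6 are evaluable); 0/7 or 1/7 does not exclude 0.29 (two-sided exact 95% upper limits 0.41 and 0.58).* Finalise this once the sponsor has reconciled the event definition across 9.1, 9.2 and 9.4.2.
2. **Section 9.4.2.** State that the exact binomial test uses the null of 0.01, so that 2 or more of 7 are needed to reject.
3. **Synopsis, 6.3 and 9.2.** Reconcile planned and actual numbers: remove 16, give the original plan as up to 10 and the actual number as 7 (4 in Cohort A, 3 remaining at 60 mg). Describe the 7 completers as the pooled set of 9.4.2, and use one definition of Initial Cohort throughout.

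The cost is text only, plus the sponsor's decision on one event definition. The document will then show openly that power at the expected proportion is below 80%. The number of participants, the cut-off and all clinical rules are unchanged.
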